Appendix 2: Study Specific Definitions

Cardiovascular disease will focus primarily on arterial thromboembolic disease processes with the following terms:

System Organ Class	Event
Cardiac	Coronary artery disease, acute coronary syndromes, ischemic cardiomyopathy, angina, and related/synonymous terms.
Nervous system	Transient ischemic attack, cerebral vascular accident, cerebral hemorrhage, and related/synonymous terms.
Surgical procedures	Coronary artery bypass grafting, angioplasty ± stent, peripheral revascularization procedures, and related/synonymous terms.
Vascular disorders	Arterial occlusive disease, arterial thromboembolic events, and related/synonymous terms.

Three major geographic regions are defined below:

Region	Countries
North America	United States, Canada
EU	All European countries
Rest of the world	All countries not included in North America and EU

EU, European Union.

Definitions for prespecified adverse events of special interest are listed below:

Event Grouping of Interest	Definition
Convulsions	Narrow SMQ of ‘convulsions’
Neutropenia	PT: neutrophil count decreased, neutropenia, white blood cell count decreased, leukopenia, agranulocytosis, cyclic neutropenia, febrile neutropenia, neutropenic infection, neutropenic sepsis, neutrophil percentage decreased, band neutrophil count decreased, band neutrophil percentage decreased, and idiopathic neutropenia
Memory impairment	All PT in MedDRA High Level Group Term ‘mental impairment disorders’
Hypertension	Narrow SMQ of ‘hypertension’
Hepatic impairment	Narrow SMQ of ‘hepatic failure, fibrosis and cirrhosis and other liver damage related conditions;’ narrow SMQ of ‘hepatitis, non-infectious;’ and narrow SMQ of ‘liver related investigations, signs and symptoms’
Major adverse cardiovascular events	Narrow SMQs of ‘myocardial infarction,’ ‘haemorrhagic cerebrovascular conditions,’ and ‘ischemic cerebrovascular conditions,’ and ‘heart failure’
PRES	Narrow SMQ of ‘noninfectious encephalopathy/delirium’

SMQ: standardized MedDRA query, PT: preferred term

PPD

[Redacted]

[Redacted]

[Redacted]

[Redacted]

[Redacted]

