The most common adverse reactions ($\geq 10\%$) that occurred more commonly ($\geq 2\%$ over placebo) in enzalutamide-treated patients from the 2 phase 3, randomized, placebo-controlled clinical studies (CRPC2, MDV3100-03) were asthenia/fatigue, back pain, decreased appetite, constipation, arthralgia, diarrhea, hot flush, upper respiratory tract infection, peripheral edema, dyspnea, musculoskeletal pain, weight decreased, headache, hypertension, and dizziness/vertigo.

In clinical studies, seizure occurred in 0.5% of patients receiving enzalutamide. Because of the risk of seizure associated with enzalutamide use, patients should be advised of the risk of engaging in any activity where sudden loss of consciousness could cause serious harm to themselves or others. Enzalutamide should be permanently discontinued in patients who develop a seizure during treatment. Posterior reversible encephalopathy syndrome (PRES), a neurologic disorder that can present with rapidly evolving symptoms including seizure, headache, lethargy, confusion, blindness, and other visual and neurologic disturbances, with or without associated hypertension, has been reported in patients receiving enzalutamide in

the postmarketing setting. Enzalutamide should be permanently discontinued in patients who develop PRES during treatment.

Additional information on the clinical experience with enzalutamide is provided in the enzalutamide investigator brochure.

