9.8.1.1. Adverse Events of Special Interest

The following TEAEs of special interests will be summarized for the overall safety population and by SOC and PT for each categorized treatment group. Additionally, for the following special adverse events, Kaplan-Meier methods will be used to display the time to the first occurrence of each of these events, if the number of events is deemed sufficiently large:

- Convulsions;
- Neutropenia;
- Cognitive and memory impairment disorders as identified by the higher-level group term for mental impairment;
- Hypertension;
- Hepatic impairment;
- Select cardiovascular events as defined in [Appendix 2](#);
- Posterior reversible encephalopathy syndrome (PRES).

A detailed list of the derivation of each term is provided in [Appendix 2](#).

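### The SAP defines its PRES row by a wider encephalopathy/delirium query, so the grouping count and any curve labelled PRES can include events that are not PRES

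*SAP*

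**What the plan says.** SAP section 9.8.1.1 (Adverse Events of Special Interest) lists seven items, the last being PRES. It says the listed events "will be summarized for the overall safety population and by SOC and PT for each categorized treatment group". It adds that "Kaplan-Meier methods will be used to display the time to the first occurrence of each of these events, if the number of events is" judged large enough. For the definitions it states: "A detailed list of the derivation of each term is provided in" Appendix 2.

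In SAP Appendix 2 (Study Specific Definitions), the table of event groupings defines the PRES row as the narrow query titled "noninfectious encephalopathy/delirium". Nothing limits the row to the PRES preferred term.

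Protocol section 1.2 describes PRES as "a neurologic disorder that can present with rapidly evolving symptoms including seizure, headache, lethargy, confusion, blindness" and other disturbances, reported after marketing. Protocol section 1.4 lists PRES by name among the important identified risks, separately from seizure and from cognitive/memory impairment.

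**The concern.** The row carries the name of one syndrome, but its rule collects a family of conditions. Anyone whose event falls under the query is counted in a total headed PRES, whether or not the event was PRES. If a time-to-first-event curve is drawn for the row, that event is also timed as PRES.

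At stake is the meaning of a safety number. PRES is a named identified risk, and its arm-level count is likely to be read from a summary table by people who do not turn to Appendix 2. If other events fill the row, the total overstates PRES. Depending on how those events fall between the arms, it could also suggest a difference that is not due to PRES, or dilute one that is.

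**Working it through.** The plan gives no PRES figure to reproduce, so the check is a comparison of texts, followed by a range calculation on assumed rates.

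**Texts side by side**

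1. *Label.* SAP 9.8.1.1 names PRES alone.
2. *Rule.* Appendix 2, which 9.8.1.1 makes the governing derivation, uses the full narrow query. By its title the query covers noninfectious encephalopathy and delirium in general.
3. *Meaning in the protocol.* Sections 1.2 and 1.4 treat PRES as a distinct disorder and a distinct risk.
4. *Neighbouring rows.* Convulsions and hypertension use queries with the same name as the row. Neutropenia is built from a list of preferred terms, so a definition at that level is already in use in this table. The PRES row puts the name of a single syndrome on a query titled for wider conditions.
5. *What is displayed.* The mixing affects the grouping total and any curve. It does not affect the preferred-term lines within the same summary. The condition on the curve, enough events, is applied to the mixed count, so events other than PRES could be what causes a curve headed PRES to be drawn.

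**How much mixing?**

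Inputs:
- Planned enzalutamide arm: 960 (SAP section 5). This is the randomized number; the tabulation uses the safety population, which may be slightly smaller.
- PRES rate: assumed, 0.01% to 0.5%.
- Rate of other events in the query: assumed, 0.05% to 2%.

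Formulas: expected patients = 960 × rate. Share of the row that is not PRES = other rate / (other rate + PRES rate), taking no patient to have both.

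| PRES rate (assumed) | Other rate (assumed) | Expected PRES | Expected other | Share not PRES |
|---|---|---|---|---|
| 0.01% | 0.05% | 0.1 | 0.5 | 83% |
| 0.01% | 2% | 0.1 | 19.2 | 99.5% |
| 0.1% | 0.1% | 1.0 | 1.0 | 50% |
| 0.1% | 1% | 1.0 | 9.6 | 91% |
| 0.5% | 0.05% | 4.8 | 0.5 | 9% |
| 0.5% | 2% | 4.8 | 19.2 | 80% |

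For example, 0.05 / (0.05 + 0.5) = 0.09 and 2 / (2 + 0.01) = 0.995. The share passes one half only when the other events are more frequent than PRES. At a PRES rate of 0.01%, the chance of seeing any PRES case in 960 patients is 1 − (1 − 0.0001)^960 = 9%.

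A range of 9% to 99.5% shows that the assumed rates determine the answer. The documents do not narrow it.

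**The case against.** The strongest reply is that the PRES count is not lost. SAP 9.8.1.1 asks for the special-interest events by system organ class and preferred term, and section 9.8.1 tabulates all treatment-emergent events the same way. An event coded to the PRES term would have its own line by arm. This stands, and it confines the problem to the grouping total and the curve.

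A second reply is that the Appendix 2 rows are meant to be sensitive groupings under short labels. Neutropenia takes in leukopenia; hepatic impairment takes in liver-related investigations, signs and symptoms. Since the protocol describes PRES as presenting with lethargy and confusion, an unrecognised case could be coded as encephalopathy or delirium, and a row built on one preferred term would miss it. This is a fair argument for keeping the query. It is not an argument for heading the query with the name of one syndrome, and the SAP does not say that the row is a screen.

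Third, the Kaplan-Meier display is conditional on event numbers and may never be produced. That also stands.

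A reader might go further and infer that the PRES row would consist mostly of other events, or would overstate PRES about tenfold. The tenfold figure follows from one choice of inputs: 1% background in 960 patients is 9.6, plus one true case is 10.6, against 1. The documents contain no such rates and no list of the query's terms, so neither statement can be made from them.

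**Conclusion.** The point holds in a limited form. The label and the derivation of the PRES row do not match, and the grouping total, with any curve drawn from it, can include encephalopathy or delirium that is not PRES. The size of the mixing cannot be set from the documents.

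A reader might conclude that the plan yields a wrong PRES rate or would conceal a true signal. The documents do not support that either, because the planned preferred-term breakdown lets PRES be read separately.

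Severity is low. The effect is confined to descriptive safety reporting; no hypothesis test, type I error allocation, power figure, analysis population or data collection is touched. The conclusion rests on two readings: that the query is as wide as its title says, and that PRES events are coded to a preferred term of that name. The SAP allows MedDRA 14.1 or any later version, so both should be confirmed in the version used.

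**What to change.** In SAP Appendix 2, define the PRES row by the posterior reversible encephalopathy syndrome preferred term, and use that definition for every count or curve labelled PRES. Keep the narrow query as a second row under its own title, noninfectious encephalopathy/delirium (including PRES), and list both rows in section 9.8.1.1.

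The cost is one changed definition line and one extra table row. Events are already coded to preferred term (SAP 9.8.1), so nothing new is collected. The one drawback is that a row built on a single term may miss PRES cases coded to another term; the retained query row is there to pick those up.
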